7.2.2. Summary Measure

Part 1

Urine PK parameters Ae total, Ae(t1-t2), AUC(0-τ) (Periods 2 and 3), AUC(0-24), AUC(0-48), fe%, and CLr, and plasma PK parameters Tmax, Tlag, and t1/2 following a single 1500 mg dose of gepotidacin (Part 1 Period 1) and two 3000 mg doses of gepotidacin (Part 1 Periods 2 and 3) in healthy adult participants will be summarized by treatment. Gepotidacin PK parameter estimates will be listed by participant and treatment.

Part 2

Urine PK parameters A_e total, $A_e(t_1-t_2)$, $AUC(0-\tau)$ (Period 2), $AUC(0-24)$, $AUC(0-48)$, $f_e\%$, and CL_r and plasma PK parameters T_{max} , T_{lag} , and $t_{1/2}$ following a single 1500 mg dose of gepotidacin (Part 2 Period 1) and two 3000 mg doses of gepotidacin at a time interval to be determined from Part 1 (Part 2 Period 2) in healthy adolescent participants will be summarized by treatment. Gepotidacin PK parameter estimates will be listed by participant and treatment.

7.2.3. Population of Interest

The secondary PK analyses will be based on the PK population for urine/plasma PK concentrations, and the PK parameter population for urine/plasma PK parameters.

7.2.4. Statistical Analyses / Methods

Details of the planned displays are provided in [Appendix 10: List of Data Displays](#) and will be based on GSK Data Standards and statistical principles.

Unless otherwise specified, endpoints/variables defined in Section 7.2 will be summarized using descriptive statistics, graphically presented (where appropriate) and listed.

Secondary urine PK parameters A_e total, $A_e(t_1-t_2)$, $AUC(0-\tau)$, $AUC(0-24)$, $AUC(0-48)$, $f_e\%$, and CL_r , and plasma PK parameters T_{max} , T_{lag} , and $t_{1/2}$ will be estimated for gepotidacin. For each of these parameters the following summary statistics will be calculated by Study Part and treatment: median, maximum, minimum, arithmetic mean, SD, 95% CI for the arithmetic mean, geometric mean, CV on geometric mean, 95% CI for the geometric mean, and SD of logarithmically transformed data.

7.2.4.1. Statistical Methodology Specification

There are no planned statistical PK analyses additional to summary statistics.

8. SAFETY ANALYSES

The safety analyses will be based on the Safety population, unless otherwise specified.

8.1. Adverse Events Analyses

The severity of AEs and SAEs will be determined by the investigator according to the US National Institute of Allergy and Infectious Diseases Division of Microbiology and Infectious Diseases (DMID) criteria for adult toxicity assessment, with the exception of serum creatinine adolescent laboratory data, which will be assessed using pediatric toxicity criteria. All reported AEs will be coded using MedDRA and summarized by system organ class (SOC) and preferred term (PT).

Adverse event severity is classified as mild (grade = 1), moderate (grade = 2), severe (grade = 3), potentially life threatening (grade = 4) or resulting in death (grade = 5). Adverse events starting after the first dose of study treatment with a missing severity will be classified as severe. If a participant reports an AE more than once within an SOC/PT, the AE with the worst-case severity will be used in the corresponding severity summaries.

Relationship to study treatment, as indicated by the investigator, is classified as “not related” or “related”. Adverse events with a missing relationship to study treatment will be regarded as “related” to study treatment. If a participant reports the same AE more than once within an SOC/PT, the AE with the worst-case relationship to study treatment will be used in the corresponding relationship summaries.

Adverse events analyses including the analysis of AEs, SAEs and other significant AEs will be based on GSK Core Data Standards. All AEs, study drug related AEs, SAEs, and AEs leading to discontinuation of study treatment or withdrawal from study will be provided in separate listings. The relationship between SOC and PT will be listed. Summary tables will be provided by SOC, PT, and maximum grade.

In summary tables where AEs are presented by SOC, PT, and maximum grade, SOCs will be sorted in descending order of the total incidence then alphabetically, PTs will be sorted in descending order of the total incidence then alphabetically within the SOC.

For completely missing or partial missing AE start date or end date, imputation rules will be applied following Section [10.4.1](#).

In addition, a summary of the number and percentage of participants with common AEs, defined as AEs with $\geq 5\%$ incidence in any treatment group, will be presented in descending order of total incidence by PT. The details of the planned displays are provided in [Appendix 10: List of Data Displays](#).

8.2. Adverse Events of Special Interest Analyses

Cardiovascular, Gastrointestinal Adverse Events and events related to Acetylcholinesterase inhibition as determined by algorithm will be considered AEs of Special Interest (AESIs). AESIs except those for Acetylcholinesterase inhibition, are flagged in the eCRF and details of events are collected on special eCRF pages. Acetylcholinesterase-Inhibition AESIs will be programmatically matched with the list of AEs specified in Section 8.2.1. In addition, there will be a manual review of AE listings to ensure accuracy and completeness of AESI reporting.

8.2.1. Acetylcholinesterase-Inhibition AESIs

Any reported AE listed in the table below with a start time no later than 12 hours after the last dose administered in each treatment period, as evaluated by the investigator as per the DMID grading criteria provided in protocol Section 10.8 Appendix 8: Division of Microbiology and Infectious Disease Adult Toxicity Tables for Adverse Event Assessment, will be programmatically identified as Acetylcholinesterase inhibition related AESI.

Table 1 List of AEs for programming to be considered due to Acetylcholinesterase-Inhibition

 • Respiratory 
 ○ Bronchospasm (acute) ○ Dyspnea ○ Bronchorrhea

 • Gastrointestinal 
 ○ Nausea ○ Vomiting ○ Diarrhea ○ GI cramping and pain

 • Cardiovascular 
 ○ Bradycardia

 • Neurological 
 ○ Seizure/Convulsions ○ Vasovagal syncope ○ Salivation ○ Lacrimation ○ Diaphoresis/sweating

AESIs will be listed and tabulated, and a Cumulative Grade will be determined, calculated by the sum of the grade of each reported AE. This enables both the number of AEs and the severity of each AE to be taken into account. For instance, if two AEs in the table above are reported, one of Grade 1 and the other of Grade 3 according to DMID, the total grade of 4 would result in a Cumulative Grade 2 per [Table 2](#) below.

Table 2 Cumulative Grading of Acetylcholinesterase AESI

	Cumulative Grade 1	Cumulative Grade 2	Cumulative Grade 3	Cumulative Grade 4
Total Grade of Signs & Symptoms	1 to 3	4 to 6	7 to 10	≥ 11

The details of the planned displays are provided in [Appendix 10: List of Data Displays](#).

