2.1. Study Rationale

Single oral doses of gepotidacin (1500 and 3000 mg) were given to patients with gonorrhea in a completed Phase II study, and both doses achieved >95% efficacy; however, *in vitro* data and pharmacokinetic (PK)/pharmacodynamic modeling revealed that a higher dose would prevent the development of resistance and cover organisms with higher minimum inhibitory concentration (MIC).

The selected total daily dose for gonorrhea is 6000 mg delivered as two 3000 mg doses given either 6 or 12 hours apart in order to keep C_{max} under a threshold of 14 µg/mL to mitigate the occurrence of adverse events (AEs) due to acetylcholinesterase (AChE) inhibition (mild and transient AEs of increased salivation, blurred vision, and slurred speech were observed following high IV doses as a 1 or 2 hour infusion during a previous study).

Although total daily oral 6000 mg doses have been given to healthy participants and patients as 2000 mg three times daily (TID) for up to 14 days and daily IV 4500 mg (equivalent to 9180 mg oral dose and based on absolute bioavailability of 46%) doses have been given to healthy participants as TID regimen for up to 10 days, the safety and PK of two 3000 mg doses given either 6 or 12 hours apart have not been characterized previously and gepotidacin has not been administered previously to adolescents. Therefore, this study will support inclusion of adolescents with a body weight ≥40 kg in future Phase III studies and will provide the safety and PK data of two 3000 mg doses separated by the selected dose intervals in Part 1 and Part 2.

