
Acetylcholinesterase (AChE) Inhibition In a mass spectrometry model performed with gepotidacin, AChE was inhibited with a concentration of inhibitor where the response (or binding) was reduced by half (inhibitory concentration) of approximately 5 $\mu\text{g/mL}$ (7.5 $\mu\text{g/mL}$ of total drug concentration).
	
At higher doses, some participants have experienced effects consistent with increased cholinergic tone, including central nervous system and GI effects (increased salivation, slurred speech, blurred vision, dizziness, light-headedness, and GI upset). These effects appear to be related to C_{max} and are significantly attenuated when C_{max} is below 14 $\mu\text{g/mL}$.
	
Coadministration of anticholinergics and administration in participants with certain concomitant conditions will be excluded.
 
Close monitoring of clinical parameters and AEs will be conducted to assess effects potentially related to AChE inhibition. The C_{max} is expected to be below 14 $\mu\text{g/mL}$ in this study.

Potential Risk of Clinical Significance	Summary of Data/Rationale for Risk	Mitigation Strategy
Rash/Hypersensitivity	
A fine, mild, generalized pruritic macular skin rash was seen in 3 of 6 participants following 10 days of dosing 1500 mg 3 times daily (see GSK Document Number 2014N198291_00 Study ID BTZ115198).
 
Rash was reported as an AE for 4 of 122 participants (3%) and consisted of mild, related urticaria; moderate, related rash maculopapular; mild, related rash; mild, related urticaria; and mild, not related arthropod bite (see GSK Document Number 2015N243789_00 Study ID BTZ116704).
 
There has been no other evidence of hypersensitivity in human participants to date.
	
Exclusion criterion: History of sensitivity to any of the study drugs, components thereof, or a history of drug or other allergy that, in the opinion of the investigator or GlaxoSmithKline medical monitor, contraindicates their participation.
 
Participant monitoring: Participants will be monitored closely for cutaneous effects throughout the study, and specialist advice will be sought as needed to evaluate any clinically significant finding.
 
Participant evaluation criteria: Grade 3 or higher rash or Grade 2 rash with evidence of systemic involvement (see Section 7.1.4).

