Diarrhea	Mild or transient; 3 to 4 loose stools/day or mild diarrhea lasting <1 week	Moderate or persistent; 5 to 7 loose stools/day or diarrhea lasting >1 week	>7 loose stools/day or bloody diarrhea; or orthostatic hypotension or electrolyte imbalance or >2L IV fluids required	Hypotensive shock or physiologic consequences requiring hospitalization
Oral discomfort/ Dysphagia	Mild discomfort; no difficulty swallowing	Some limits on eating/drinking	Eating/talking very limited; unable to swallow solid foods	Unable to drink fluids; requires IV fluids

IV=intravenous.

NEUROLOGICAL				
	Grade 1	Grade 2	Grade 3	Grade 4
Neuro-Cerebellar	Slight incoordination dysdiadochokinesis	Intention tremor, dysmetria, slurred speech; nystagmus	Locomotor ataxia	Incapacitated
Psychiatric	Mild anxiety or depression	Moderate anxiety or depression; therapy required; change in normal routine	Severe mood changes requiring therapy; or suicidal ideation; or aggressive ideation	Acute psychosis requiring hospitalization; or suicidal gesture/attempt or hallucinations
Muscle strength	Subjective weakness; no objective symptoms/signs	Mild objective signs/symptoms; no decrease in function	Objective weakness; function limited	Paralysis
Paresthesia (burning, tingling, etc.)	Mild discomfort; no treatment required	Moderate discomfort; non-narcotic analgesia required	Severe discomfort; or narcotic analgesia required with symptomatic improvement	Incapacitating; or not responsive to narcotic analgesia
Neurosensory	Mild impairment in sensation (decreased sensation, e.g., vibratory, pinprick, hot/cold in great toes) in focal area or symmetrical distribution; or change in taste, smell, vision, and/or hearing	Moderate impairment (moderately decreased sensation, e.g., vibratory, pinprick, hot/cold to ankles) and/or joint position or mild impairment that is not symmetrical	Severe impairment (decreased or loss of sensation to knees or wrists) or loss of sensation of at least moderate degree in multiple different body areas (i.e., upper and lower extremities)	Sensory loss involves limbs and trunk; paralysis; or seizures

MUSCULOSKELETAL				
	Grade 1	Grade 2	Grade 3	Grade 4
Arthralgia (joint pain)	Mild pain not interfering with function	Moderate pain, analgesics and/or pain interfering with function but not with ADL	Severe pain; pain and/or analgesics interfering with ADL	Disabling pain

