2. SUMMARY OF KEY PROTOCOL INFORMATION

2.1. Changes to the Protocol Defined Statistical Analysis Plan

Changes to the planned statistical analysis specified in the protocol (Dated: 13-JUN-2019) are listed below.

[figure not shown]
- For adolescent serum creatinine lab data, pediatric DMID toxicity criteria will be used.
- Events associated with acetylcholinesterase inhibition will be programmatically and manually assessed as adverse events of special interest (AESIs). See analysis plan in Section 8.2 and Section 10.4.3.
- Section 7.1.1.2 of this analysis plan specifies that the accumulation ratio R_o AUC will be calculated as $AUC(0-\tau)$ after the second dose divided by $AUC(0-\tau)$ after the first dose (rather than using $AUC(0-6)$ as stated in the protocol), to make this formula widely applicable to all dosing intervals.

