10.10.9. ICH Listings

ICH : Listings					
No.	Population	IDSL / TST ID / Example Shell	Title	Programming Notes	Deliverable [Priority]
Randomization					
1	Randomized	CP_TA1	Listing of Randomised and Actual Treatment		SAC [1]
Subject Disposition					
2	Safety	ES3	Listing of Reasons for Study Withdrawal		SAC [1]
3	Safety	SD3	Listing of Reasons for Study Treatment Discontinuation		SAC [1]
4	Randomized	BL1	Listing of Subjects for Whom the Treatment Blind was Broken During the Study		SAC [1]
5	Screened	ES7	Listing of Reasons for Screening Failure		SAC [1]
6	Enrolled	DV2	Listing of Important Protocol Deviations		SAC [1]
7	Screened	IE4	Listing of Subjects with Inclusion/Exclusion Criteria Deviations		SAC [1]
8	Safety	SP3	Listing of Subjects Excluded from Any Population		SAC [1]
9	Safety	SAFE_L1	Listing of Subjects in Previous Clinical Trial		SAC [1]
Demographics					
10	Safety	DM4	Listing of Demographic Characteristics	Include height, weight and BMI	SAC [1]
11	Safety	DM10	Listing of Race		SAC [1]
Medical Conditions and Concomitant Medications					
12	Safety	MH3	Listing of Medical Conditions		SAC [1]
13	Safety	CM4	Listing of Concomitant Medications		SAC [1]

ICH : Listings					
No.	Population	IDSL / TST ID / Example Shell	Title	Programming Notes	Deliverable [Priority]
Exposure					
14	Safety	SAFE_L2	Listing of Exposure Data		SAC [1]
Safety					
15	Safety	AE2	Listing of Relationship Between System Organ Class and Verbatim Text		SAC[1]
16	Safety	AE7	Listing of Subject Numbers for Individual Adverse Events		SAC [1]
17	Safety	AE9CP	Listing of All Adverse Events		SAC [1]
18	Safety	AE9CP	Listing of Study Drug Related Adverse Events		SAC [1]
19	Safety	AE9CPA	Listing of Serious Adverse Events		SAC [1]
20	Safety	AE9CP	Listing of Adverse Events Leading to Withdrawal from Study		SAC [1]
21	Safety	SAFE_L3	Listing of Cardiovascular Adverse Events of Special Interest	Conditional display	SAC [1]
22	Safety	SAFE_L4	Listing of Gastrointestinal Adverse Events of Special Interest	Conditional display	SAC [1]
23	Safety	SAFE_L5	Listing of Acetylcholinesterase-Inhibition Adverse Events of Special Interest	Conditional display, Flag events with onset time of 0-6hr post last dose	SAC [1]
24	Safety	SAFE_L6	Listing of Non-Gastrointestinal Acetylcholinesterase-Inhibition Adverse Events of Special Interest.	Conditional display, Flag events with onset time of 0-6hr post last dose	SAC[1]

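### The programmed list for acetylcholinesterase-inhibition AESIs omits four of the five non-GI cholinergic effects that the protocol itself names

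*SAP*

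**What the plan says.** Protocol 2.1 explains the split dose by the wish to limit AChE-related events, and reports that "mild and transient AEs of increased salivation, blurred vision, and slurred speech were observed following high IV doses". The risk table in Protocol 2.3.1 gives a longer set of effects seen at higher doses, "including central nervous system and GI effects (increased salivation, slurred speech, blurred vision, dizziness, light-headedness, and GI upset", and says that they appear related to Cmax and are much reduced below 14 µg/mL.

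The SAP adds an AChE analysis that the protocol did not have. SAP 2.1 says: "Events associated with acetylcholinesterase inhibition will be programmatically and manually assessed as adverse events of special interest". Under SAP 8.2.1 the programmed rule is "Any reported AE listed in the table below with a start time no later than 12 hours after the last dose" in each treatment period. Table 1 then lists the qualifying terms:

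- respiratory: bronchospasm, dyspnea, bronchorrhea;
- gastrointestinal: nausea, vomiting, diarrhea, cramping and pain;
- cardiovascular: bradycardia;
- neurological: seizure, vasovagal syncope, salivation, lacrimation, sweating.

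The DMID grades of the qualifying events are summed and banded into a Cumulative Grade by SAP Table 2. SAP 8.2 also says: "In addition, there will be a manual review of AE listings to ensure accuracy and completeness of AESI reporting". The results go to Tables 2.5 and 2.6, Figure 2.2 and Listings 23 to 25. Listing 24 is titled "Listing of Non-Gastrointestinal Acetylcholinesterase-Inhibition Adverse Events of Special Interest".

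**The concern.** The AChE displays exist to show the effects that the 14 µg/mL threshold is meant to limit. The programmed list leaves out most of the specific non-GI effects on which the protocol bases that threshold, and the SAP gives no reason. A participant whose only cholinergic signs are the omitted ones is not an AESI unless someone adds the events by hand. A participant with some listed and some omitted signs can be given too low a Cumulative Grade.

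Listing 24 is the most exposed. It is the view least affected by non-specific GI events, yet salivation is the only protocol-named effect that the list lets into it. The GI terms count whatever their cause, so total AESI counts need not be low. What is at risk is whether these displays describe the drug's documented cholinergic pattern. Safety is among the study's primary objectives.

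**Working it through.** **Comparing the lists.** The left column holds the effects named in Protocol 2.3.1.

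| Effect | Also in Protocol 2.1 | In SAP Table 1 |
|---|---|---|
| Increased salivation | yes | yes |
| Slurred speech | yes | no |
| Blurred vision | yes | no |
| Dizziness | no | no |
| Light-headedness | no | no |
| GI upset | no | yes, through the four GI terms |

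Omitted: 4 of the 6 effects in 2.3.1 (3 of 5 if dizziness and light-headedness are one concept), 2 of the 3 in 2.1, and 4 of the 5 non-GI effects. Table 1 has 3 + 4 + 1 + 5 = 13 terms, of which 9 are non-GI, and only salivation among those 9 is named in either protocol section. Vasovagal syncope is a different event from dizziness.

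**The SAP's grading rule.** SAP Table 2 bands the summed grades as 1 to 3, 4 to 6, 7 to 10, and 11 or more for Cumulative Grades 1 to 4. The SAP's own example reproduces: 1 + 3 = 4, Cumulative Grade 2.

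**Grades used.** The DMID table in Protocol Appendix 8 places slurred speech in its Grade 2 column ("Intention tremor, dysmetria, slurred speech; nystagmus") and a change in vision in its Grade 1 column. Protocol 2.1 describes the observed effects as mild, so slurred speech is taken as 1 to 2. Blurred vision, salivation and dizziness are assumed to be Grade 1.

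| Events in one participant | Programmed total | Total with terms added |
|---|---|---|
| Slurred speech + blurred vision | 0, no AESI | (1 or 2) + 1 = 2 or 3, Cumulative Grade 1 |
| The same + salivation | 1, Cumulative Grade 1 | 3 or 4, Cumulative Grade 1 or 2 |
| The same + dizziness | 1, Cumulative Grade 1 | 4 or 5, Cumulative Grade 2 |

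The second case reaches Cumulative Grade 2 only if slurred speech is Grade 2. The third reaches it even if every event is mild. If light-headedness were also reported and counted apart from dizziness, the third case would total 5 or 6, still Cumulative Grade 2.

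**Effect on an incidence.** With 14 participants on active treatment in each part, one reclassified participant changes an incidence by 1/14 = 7.1 percentage points.

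**What the manual review specifies.** SAP 2.1 refers to 8.2 and 10.4.3 for the plan. Section 8.2 gives the single sentence quoted above. Section 10.4.3 only names AChE events as a category. Neither gives terms, criteria or a reviewer. Section 8.2 describes these AESIs as set by algorithm and says that, unlike the cardiovascular and GI AESIs, they are not flagged in the eCRF. The Cumulative Grade example refers to events in Table 1.

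**The 0 to 6 hour flag.** The programming note for Listings 23 and 24 reads "Flag events with onset time of 0-6hr post last dose". The 12-hour rule already takes in first-dose events, but read literally the flag would not mark those near the first-dose peak in a two-dose period.

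**The case against.** The strongest reply is that the SAP provides a safeguard. A review meant to ensure completeness exists to catch events that the algorithm misses, and with about 17 participants per part every AE can be read. SAP 8.2.1 also says that AESIs are tabulated and their grades summed, so an event accepted by hand would naturally be counted. This narrows the gap without closing it. With no terms or criteria, one person could take the task as checking the matches and another as adding new concepts, and the displays would then differ.

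Second, nothing is lost from safety reporting. The omitted events appear in Tables 2.1 and 2.2 (the latter if judged drug-related), Listing 17 and Figure 2.3, which shows events within individual participants. A single non-serious event in an active group of 14 would also pass the 5% threshold for Table 2.3, if groups are summarised by part. This stands, and it limits the consequence to the AChE-specific displays.

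Third, the size is illustrative. The documents give no frequency for these combinations. Protocol 2.3.1 expects Cmax below 14 µg/mL, and Protocol 4.3 expects less than 3% of the population to exceed it. This also stands: the regrading cases show what the rule does, not how often it will happen.

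Finally, counting dizziness and light-headedness as one concept departs from a plain sum over reported events, and the flag's reference dose can be read as the most recent dose. Both are side issues and leave the mismatch as it is.

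**Conclusion.** The concern holds. SAP Table 1 and Protocol 2.3.1 disagree on which events represent cholinergic effects of this drug, and the unspecified manual review does not reconcile them. As programmed, a participant with two of the three effects cited in Protocol 2.1 scores 0. One with salivation, slurred speech, blurred vision and dizziness is placed in Cumulative Grade 1 where the full set gives Grade 2.

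These results rest on the assumed grades above and on no event being added by hand. The finding should be fixed but has limited reach: it affects final descriptive displays only. It does not touch AE collection, the PK endpoints or the Part 2 interval choice, which under SAP 3.1 uses data management listings and WinNonlin outputs. Confidence is high that the terms are missing; how many participants would be affected cannot be known from the documents.

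**What to change.** Before the final unblinding, amend SAP 8.2 and 8.2.1 as follows:

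- Add blurred vision/visual disturbance, slurred speech/dysarthria and dizziness/light-headedness to Table 1, each with the MedDRA preferred terms to be matched, or state why they are left out.
- Count dizziness and light-headedness as one concept in the grade sum, so that one complaint is not scored twice.
- State the criteria for the manual review, and that events it adds count toward the Cumulative Grade.
- Apply the revised definition to Tables 2.5 and 2.6, Figure 2.2 and Listings 23 to 25.
- Set the 0 to 6 hour flag in Listings 23 and 24 relative to the most recent dose.

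The cost is SAP wording and a few lines of programming, with no new data. The added terms come from the protocol, so the change does not depend on study results. The downside is that AESI counts may rise slightly, because dizziness is non-specific.

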10.10.5. Safety Tables

Safety Tables					
No.	Population	IDSL / TST ID / Example Shell	Title	Programming Notes	Deliverable [Priority]
Adverse Events					
2.1	Safety	AE5B	Summary of Adverse Events by System Organ Class and Preferred Term and Maximum Grade		SAC [1]
2.2	Safety	AE5B	Summary of Drug- Related Adverse Events by System Organ Class and Preferred Term and Maximum Grade		SAC [1]
2.3	Safety	AE15	Summary of Common (>=5%) Non-serious Adverse Events by System Organ Class and Preferred Term (Number of Subjects and Occurrences)		SAC [1]
2.4	Safety	AE16	Summary of Serious Adverse Events by System Organ Class and Preferred Term (Number of Subjects and Occurrences)		SAC [1]
2.5	Safety	AE5B	Summary of Acetylcholinesterase-Inhibition Adverse Events of Special Interest by System Organ Class and Preferred Term and Maximum Grade		SAC[1]
2.6	Safety	SAFE_T1	Summary of Cumulative Grades of Acetylcholinesterase-Inhibition Adverse Events of Special Interest		SAC [1]
Laboratory Measurements					
2.7	Safety	LB1	Summary of Chemistry Change from Baseline		SAC [1]
2.8	Safety	LB1	Summary of Hematology Change from Baseline		SAC [1]
2.9	Safety	UR3	Summary of Urinalysis Dipstick Results		SAC [1]
2.10	Safety	LIVER1	Summary of Liver Monitoring/Stopping Event Reporting		SAC [1]
Electrocardiograms					
2.11	Safety	EG1	Summary of ECG Findings		SAC [1]

2.12	Safety	SAFE_T2	Summary of Frequency of Maximum Post-Dose ECG Parameter Corrected QTc Interval		SAC [1]
2.13	Safety	SAFE_T3	Summary of Frequency of Maximum Change from Baseline for ECG Parameter Corrected QTc Interval		SAC [1]
2.14	Safety	EG2	Summary of Change from Baseline in ECG Values		SAC [1]
Vital Signs					
2.15	Safety	VS1	Summary of Change from Baseline in Vital Signs		SAC [1]
Cardiovascular Risk Factors					
2.16	Safety	FH1	Summary of Family History of Cardiovascular Risk Factors		SAC [1]
2.17	Safety	SU1	Summary of Substance Use		SAC [1]

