10.10.6. Safety Figures

Safety Tables					
No.	Population	IDSL / TST ID / Example Shell	Title	Programming Notes	Deliverable [Priority]
Adverse Events					
2.1	Safety	AE10	Gastrointestinal Adverse Events of Special Interest Adverse Events	Part 1, Part 2, and combined	SAC [1]
2.2	Safety	SAFE_F1	Plot of Distribution of Cumulative Grades of Acetylcholinesterase-Inhibition Adverse Events of Special Interest	Combine Part 1 and Part 2 in one page	SAC [1]
2.3	Safety	SAFE_F2	Plot of duration and severity of Adverse Events for Individual Participants	Part1 and Part 2	SAC [1]

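### Does the Cumulative Grade for acetylcholinesterase-inhibition events hide a severe single event?

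*SAP*

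**What the plan says.** SAP 8.2.1 sums the DMID grades of all qualifying acetylcholinesterase-inhibition events. Its Table 2 bands the total: 1 to 3 is Cumulative Grade 1, 4 to 6 is 2, 7 to 10 is 3, and 11 or more is 4. The stated reason is "This enables both the number of AEs and the severity of each AE to be taken into account". The worked example takes one Grade 1 and one Grade 3 event: "the total grade of 4 would result in a Cumulative Grade 2".

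By title, two displays carry the score: Table 2.6, "Summary of Cumulative Grades of Acetylcholinesterase-Inhibition Adverse Events of Special Interest" (SAP 10.10.5), and Figure 2.2, "Plot of Distribution of Cumulative Grades of Acetylcholinesterase-Inhibition Adverse Events of Special Interest" (SAP 10.10.6). Several others show the underlying grades:

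- Table 2.5, "Summary of Acetylcholinesterase-Inhibition Adverse Events of Special Interest by System Organ Class and Preferred Term and Maximum Grade", stands directly before Table 2.6.
- Figure 2.3 is the "Plot of duration and severity of Adverse Events for Individual Participants".
- Listing 17 is the "Listing of All Adverse Events", and Listing 23 is the "Listing of Acetylcholinesterase-Inhibition Adverse Events of Special Interest".
- Listing 25 presents the same events by treatment and by each participant's maximum grade. Like Listing 23, it is marked as a conditional display.

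**The concern.** SAP 8.1 uses grades 1 to 4 for mild, moderate, severe and potentially life-threatening events. SAP 8.2.1 then uses Grade 1 to 4 again for a different quantity and does not say that the two scales differ. Someone who opens only Table 2.6 or Figure 2.2 could take Cumulative Grade 1 to mean mild, although it may contain a participant whose one event was severe.

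The stake would be a safety summary that looks milder than the data. Acetylcholinesterase inhibition is a named risk in Protocol 2.3.1, and safety is a primary objective in both parts.

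**Working it through.** **Inputs.** The summing rule and cut-points come from SAP 8.2.1, Table 2. The meaning of single-event grades comes from SAP 8.1. With t the sum of grades:

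band(t) = 1 if t ≤ 3; 2 if 4 ≤ t ≤ 6; 3 if 7 ≤ t ≤ 10; 4 if t ≥ 11.

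**Step 1: the SAP's example.** t = 1 + 3 = 4, so band(4) = 2. This agrees with the SAP, so there is no arithmetic error.

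**Step 2: lone events.**

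| Single event | Total | Cumulative Grade |
|---|---|---|
| Grade 1 | 1 | 1 |
| Grade 2 | 2 | 1 |
| Grade 3 | 3 | 1 |
| Grade 4 | 4 | 2 |

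A lone Grade 3 shares its label with a lone Grade 1. A lone Grade 4 shares its label with four Grade 1 events (1 + 1 + 1 + 1 = 4).

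**Step 3: all sets of one to four events with grades 1 to 4.** Each set's band is compared with its own worst grade.

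| Events in set | Sets | Below worst | Equal | Above | Sets with a Grade 3 or 4 | Of these, below worst |
|---|---|---|---|---|---|---|
| 1 | 4 | 3 | 1 | 0 | 2 | 2 |
| 2 | 10 | 8 | 2 | 0 | 7 | 7 |
| 3 | 20 | 10 | 10 | 0 | 16 | 10 |
| 4 | 35 | 8 | 22 | 5 | 30 | 8 |

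For one or two events, 2 + 7 = 9 of 9 sets with a severe event are labelled below it. With four events, 5 sets are labelled above their worst grade; four Grade 1 events give Cumulative Grade 2. A score that mixes number and severity should move both ways. These are counts of possible patterns, not probabilities.

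**Step 4: the pattern previously seen.** Protocol 2.1 describes the earlier cholinergic events as mild and transient. For one to three Grade 1 events the total is 1 to 3, so the Cumulative Grade is 1 and equals the worst grade.

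**Step 5: what a change would do.** With the worst grade shown beside the score, a lone Grade 3 would read Cumulative 1, maximum 3; a lone Grade 4 would read Cumulative 2, maximum 4; the SAP example would read Cumulative 2, maximum 3. No score changes, because the low label comes from the sum and cut-points and not from a missing column. Raising the score to at least the worst grade would change labels, but max(band, worst) equals the worst grade in 4 + 10 + 20 + 30 = 64 of 69 sets. It would largely duplicate maximum grade and lose the count of events.

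**Step 6: use of the score.** SAP 2.4 states that no hypothesis is tested. SAP 3.1 bases the review between parts on data listings and PK software output. SAP 10.10.3 names one delivery, the final analysis, and Table 2.6 and Figure 2.2 are assigned to it.

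**The case for a change.** The best case for a change starts from concrete events. SAP Table 1 lists seizures, and Protocol Appendix 8 counts seizures among events to be graded 4. A participant whose only listed event is a seizure would be Cumulative Grade 2, level with four mild events. SAP 8.1 also treats a post-dose event with missing severity as severe. If that were the only listed event and the imputed grade entered the sum, the cautious imputation would end as Cumulative Grade 1. By their titles, none of the other displays links a participant's Cumulative Grade to that participant's worst grade. The remedy is cheap: two sentences, a column or two, and a marker on a figure.

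The arithmetic in this stands, and so does the chance of misreading Table 2.6 in isolation. The rest carries less weight. SAP 8.2.1 gives the score its own name, its own table and a stated purpose, and its example already places a Grade 3 event in Cumulative Grade 2. The seizure would still appear at Grade 4 in Table 2.5. With about 14 active participants per part, a cross-tabulation would be mostly empty cells or single people, whose grades the listings already give. The layouts of Table 2.6 and Figure 2.2 are not in the documents, so it cannot be said that they lack a clarifying column or note.

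One gap is real: SAP 8.2.1 does not say whether grades are summed per participant or per participant within a treatment period. The event window is set relative to the last dose in each period, and Listing 25 is organised by treatment. An analyst would naturally sum within participant and treatment. This is missing detail, not a wrong method.

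**Conclusion.** No change to the plan is called for. The effect is real but confined by title to the labels in two descriptive displays: 9 of 9 one- or two-event sets containing a Grade 3 or 4 read below their worst event. The rule is disclosed, it serves its stated purpose, and it hides no severe event.

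This rests on three assumptions: that Table 2.5 is produced as titled, that the conditional Listings 23 and 25 are produced when such events occur, and that the score informs no decision beyond those the documents describe. A footnote saying that Cumulative Grade is a burden score, pointing to Table 2.5 and Listing 25 and naming the summing unit, would help a casual reader. That is editorial, and no result or conclusion depends on it.
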